10.2 Statistical analysis

10.2.1 Main analysis

An intention to treat analysis will be performed. In particular, children randomised to nonsurgical conventional medical treatment will be retained in that group for the analysis even if they subsequently receive a tonsillectomy.

The primary clinical outcome measure will be the number of episodes of sore throat. This variable will be analysed using generalised linear modelling assuming a Poisson error structure with a log link function⁵¹. By fitting the difference between the two experimental groups as a fixed effect, interval estimates of the effect of tonsillectomy (in each of the first two years of follow up) will be generated. These estimates will then be used in the economic analysis.

The same approach will be used to analyse the other outcomes. A Poisson error structure will be assumed for data in the form or a count (such as the number of episodes of absence from school) and normal error structure adopted for continuous variables (such as the quality of life indices).

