3.4 Outcome measurement

The primary clinical outcome is the reported number of episodes of sore throat in the two years after randomisation.

Secondary clinical outcomes include reported number of episodes of sore throat, otitis media and upper respiratory tract infection which invoke a GP consultation; reported number of symptom-free days; reported severity of sore throats and surgical and anaesthetic morbidity. In addition to the measurement of these clinical outcomes, the impact of the treatment on costs and quality of life will be assessed. There will also be an economic evaluation.

4 Subject selection

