4.3 Number of subjects required

We estimate a completed sample size at follow up of 284 children. Allowing for an attrition rate of around 30% we will need to recruit a total of 406 children to the trial to achieve the estimated sample of 284 (who will complete the trial). Within the study hospitals some 1700 tonsillectomies/adeno-tonsillectomies are currently performed annually. Only two thirds of these will have recurrent sore throats. In any trial where the intervention is widely used in current practice there are likely to be large numbers of eligible participants who opt for the intervention treatment and decline participation in the trial. We estimate that this could be up to one half of all eligible referrals from primary care. The maximum available for randomisation is therefore estimated as 566 per annum. Loss of eligible subjects in the trial is expected due to holiday periods and 'winter pressures'. On the experience of loss in other trials (50%) a conservative estimate would be 283 per annum. If we assume a conservative rate of attrition of 30% over two years we would expect 198 completing trial participants to be recruited in a 12 month period. Given seasonal effects a full 2 years would be necessary to recruit the estimated sample size.

The cohort sample will be identified from participants who indicated a preference not to be randomised within the trial and who agreed to data collection. An appropriate sampling fraction will be used once non-participation in the trial can be estimated.

5 Subject recruitment

Recruitment to the study will take place in secondary care. All GP referrals to study centres of children with recurrent sore throat will be considered by participating surgeons. Arrangements are in place in each centre for eligible children to be referred to the clinical applicants. GPs will be informed of this reorganisation. This will facilitate efficient use of outpatients clinics at which trial participants would be recruited.

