9.1 Data to be collected

All participants will be followed-up for 24 months from the date of initial randomisation. To minimise recall bias, data on sore throats will be gathered by a simple, structured daily health diary completed and returned by participants on a monthly basis for 24 months. Experience of similar studies suggests that with appropriate telephone reminders 90% of diaries will be returned completed.

In addition simple outcome questionnaires will be administered to trial and cohort study participants. Overall we anticipate an 80% response rate. Interview surveys will be done at 3, 12 and 24 months after randomisation. A baseline questionnaire will be completed by all participants upon recruitment to the trial. The greater frequency of data collection in the first 12 months is necessary in order to capture data on expected changes in direct and social costs to participants in the first 12 months. Experience also suggests that data on consultation rates and prescribed medication can be gathered most accurately and reliably from medical records. Manual abstraction will be performed by trained research nurses at the end of follow up for all participants

| Primary clinical outcome | Measurement method | When | Where |
|---|---|---|---|
| Number of events of recurrent sore throat | Self-completed diary (by parent or child) | Daily recording but collected four-weekly for 24 months | Participants' homes |
| Secondary clinical outcomes | Measurement method | When | Where |
| Number of events of recurrent sore throat, otitis media or URTI recorded by GPs | GP records | End of 24 month follow-up period | General practices (GP records) |
| Adverse events: re-referral for tonsillectomy; number of symptom-free days | Self-completed diary (by parent or child) and GP records | Daily recording but collected four-weekly for 24 months and end of 24 month follow-up period | Participants' homes (diary) and general practices (GP records) |

Table 1 Clinical outcome measures for trial and cohort studies

Table 2 Measuring treatment impact

| Impact | Measure | When | Where |
|---|--|-------------------------------------|--------------------|
| Costs to participants of the condition and its management | Questionnaire to children and parents | Base-line, 3, 12 and 24 months | Participant's home |
| Social costs: e.g. time off school and parental time off work | Self-completed diary (by parent or child) | Base-line, 3, 12 and 24 months | Participant's home |

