11.2 Withdrawal of participants

Any participants wishing to withdraw from the study may do so at any time.

12 Interim analysis and data monitoring

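### The primary Poisson model counts sore-throat episodes with no term for observed diary time, although the protocol expects about 30% attrition and about 10% of diaries unreturned

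*Protocol*

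**What the plan says.** Section 3.4 defines the outcome over a fixed window: "The primary clinical outcome is the reported number of episodes of sore throat in the two years after randomisation". Section 9.1 collects it by daily diary, returned about monthly for 24 months.

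Section 10.2.1 then fixes the analysis. The response is a count: "The primary clinical outcome measure will be the number of episodes of sore throat". The model is given next: "This variable will be analysed using generalised linear modelling assuming a Poisson error structure with a log link function". The treatment group is a fixed effect, and "interval estimates of the effect of tonsillectomy (in each of the first two years of follow up) will be generated". Their onward use is explicit: "These estimates will then be used in the economic analysis". The analysis is to be by intention to treat. The section explains this through children allocated to medical care who later have surgery; it does not address missing diaries.

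Three other places say that the window will often not be fully observed:
- 4.3: "Allowing for an attrition rate of around 30% we will need to recruit a total of 406 children".
- 9.1: the expectation that with "telephone reminders 90% of diaries will be returned completed".
- 11.2: "Any participants wishing to withdraw from the study may do so at any time".

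The protocol nowhere gives an offset, a person-time denominator or a rule for incomplete diaries.

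**The concern.** A log-link Poisson model of totals compares like with like only if every total covers the same length of time, or if the model carries the log of observed time. Here the protocol itself predicts unequal observation. A child who stops the diary at month 6 contributes six months of episodes. Without an exposure term, that total is treated as if it covered the full window.

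Three things are at stake:
- **Absolute yearly differences.** These shrink even when loss is equal in the two arms, and most in year 2 because losses accumulate. They matter because the yearly estimates go to the economic analysis, and 9.1.1.2 takes the number of sore-throat events as a measure of benefit.
- **Precision.** Variation in observed time adds variation between children that a Poisson variance does not include.
- **The rate ratio.** It is biased if loss differs by arm.

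**Working it through.** **The plan's own figures.** Difference 1.5 school days, SD 4.5, 80% power, 5% two-sided: 2 x 7.849 x (4.5/1.5)^2 = 141.3, so 142 per arm and 284 in total. Then 284/0.70 = 405.7, so 406. Both reproduce, and nothing below changes them.

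**Inputs from the protocol.** Attrition d = 0.30 (4.3); diary return 0.90 (9.1); anticipated year-2 difference of about 2 episodes (10.1).

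**Assumptions.** Drop-out is uniform over 24 months. The 90% applies to diaries due while a child is still in follow-up. All 406 are analysed and partial counts are used as they stand.

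**Share of time observed.** Half of those who drop out leave in year 1 and half in year 2, so:
- Year 1: 1 - 0.25d = 0.925; x 0.90 = 0.8325.
- Year 2: 1 - 0.75d = 0.775; x 0.90 = 0.6975.
- Two years: 1 - d/2 = 0.85; x 0.90 = 0.765.

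**Effect on the year-2 difference, equal loss.** 2.0 x 0.6975 = 1.395, about 1.4. The range over other assumptions is:

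| Assumption | Year-2 time observed | Difference of 2.0 appears as |
|---|---|---|
| All losses at or before month 12 | 0.70 x 0.90 = 0.63 | 1.26 |
| Uniform loss | 0.6975 | 1.40 |
| Uniform loss, every diary returned | 0.775 | 1.55 |
| All losses at month 24 | 0.90 | 1.80 |

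**Effect on the rate ratio.** The ratio without an offset is the true ratio multiplied by (surgery exposure)/(control exposure). The diary-return factor cancels if it is equal by arm.

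| Loss, surgery v control | Two years | Year 2 |
|---|---|---|
| 30% v 30% | 1.00 | 1.00 |
| 25% v 35% | 0.875/0.825 = 1.06 | 0.8125/0.7375 = 1.10 |
| 20% v 40% | 0.90/0.80 = 1.125 | 0.85/0.70 = 1.21 |
| 35% v 25% | 0.825/0.875 = 0.94 | 0.7375/0.8125 = 0.91 |
| 40% v 20% | 0.80/0.90 = 0.89 | 0.70/0.85 = 0.82 |

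**Effect on the standard error, equal loss.** For rate r per year and observed time T, the variance of the count is r E(T) + r^2 Var(T), against the Poisson value r E(T). The ratio is 1 + r Var(T)/E(T). Before diary return, E(T) = 1.7 years and E(T^2) = 0.7 x 4 + 0.3 x 4/3 = 3.2, so Var(T) = 3.2 - 2.89 = 0.31. Scaling T by 0.90 and assuming r = 3 per year (the protocol gives no control rate), the ratio is 1 + 3 x 0.81 x 0.31/1.53 = 1.49. The true standard error is therefore about 1.22 times the Poisson one, and a nominal 5% test rejects about 11% of the time.

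**Simulation.** 203 per arm, 3 episodes per year in both arms (no true effect), 26 four-weekly diaries each returned with probability 0.90, two-sided 5%, 4,000 runs per case:

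| Loss, surgery v control | Rate ratio, no offset | Type I error, no offset | Type I error, offset |
|---|---|---|---|
| 30% v 30% | 1.00 | 12% | 4% |
| 25% v 35% | 1.06 | 31% | 6% |
| 20% v 40% | 1.13 | 71% | 5% |

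With the offset the rate ratio was 1.00 in all three cases. The simulated counts are Poisson given observed time, so the table isolates the effect of unequal exposure.

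**Completers only.** 406 - 284 = 122 randomised children are left out. Those who stay still return only about 90% of their diaries, so the exposure problem remains among them.

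**The case against.** The strongest reply is that this is detail for a statistical analysis plan, which is not shown here. An offset and rules for incomplete diaries are often placed there, and a log-link Poisson model can take an offset without altering a sentence of 10.2.1. That stands in part: the analysis may already be done correctly. But the protocol does more than stay silent. It fixes the response as a count and names the error structure, link and treatment term, for data that it predicts will be unequally observed.

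Several stronger readings are tempting and are not supported:
- *Missing diaries are set to zero episodes.* No section says so. This is only what happens if partial counts are used as they stand, and sizing on 284 completers leaves a completers-only analysis equally possible.
- *A completers-only analysis flatly contradicts intention to treat.* Section 10.2.1 explains the principle only through crossover to surgery. Dropping 122 randomised children sits badly with it, but the wording does not exclude it.
- *The benefit of surgery will be understated.* With equal loss the rate ratio is unbiased. If loss differs, its direction is unknown. Control families who wanted surgery may withdraw, but section 13 leaves surgery open to them and 10.2.1 keeps them in their arm. Children who are well after surgery may equally stop keeping diaries.
- *Section 11.1 implies better diary retention in the surgery arm.* Its nurse follow-up there most naturally concerns having the operation, and the diary reminders in the same paragraph are not limited to one arm.

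**Conclusion.** The concern holds in conditional form. As written, the primary model has no term for observed diary time, and neither way of running it is satisfactory.

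Using partial counts with equal 30% loss, uniform drop-out and 90% diary return, the anticipated year-2 difference of 2 would appear as about 1.4 (1.26 to 1.80 over the assumptions shown). That is below the two fewer episodes a year which section 1.3 reports surgeons would require. The rate ratio is then unbiased, but its standard error is too small by a factor of about 1.22 if the control rate is 3 per year. Unequal loss biases the two-year ratio by factors of about 0.89 to 1.125 in the cases examined. The size and direction of any imbalance are assumptions, not protocol figures. Using completers only avoids partial counts from children who leave, but discards about 122 randomised children and does not handle missed diaries among those who stay.

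**What to change.** In 10.2.1, model the episode rate. Add the log of days covered by returned diaries as an offset, separately for years 1 and 2. Include every randomised child with any diary data, in the allocated arm, and report by arm how many have none. Derive the absolute yearly differences for the economic analysis from the modelled rates rather than from raw mean counts.

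Add a sensitivity analysis for missing diary months. GP-recorded sore-throat consultations, which 9.1 already abstracts for all participants, may inform it but cannot replace diary episodes, because they miss episodes managed at home.

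The cost is a change of wording and a little more analysis; the diaries and GP records are already collected and the sample size stays as it is. The downside is that an offset assumes unobserved months resemble observed ones. Sore throats are seasonal (section 1) and are expected just after surgery (12.3), so the sensitivity analysis should take account of calendar season and time since surgery. If a statistical analysis plan already contains the offset, aligning the protocol sentence with it is enough on that part.

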10.1 Sample size calculation

In this trial we anticipate a fairly large difference in the primary clinical outcome (the reported number of episodes of sore throat in the two years after randomisation) with an effect size of around 1.0, but a smaller difference in a number of psycho-social outcomes including health-

related quality of life, with an effect size of 0.33. No standard sample size formula is available for economic evaluations, and a number of methods have been proposed ⁴⁸⁻⁵⁰. The information which is currently available limit the use of such methods in practical applications. Published data¹⁸ suggest that tonsillectomy may lead to a reduction of approximately 1.5 days per year in missed schooling. Given a reported standard deviation of 4.5, to detect this difference with 80% power we would need approximately 142 children in each arm of the trial assuming a significance level of 5%. A sample size of 142 children in the cohort group will allow us to detect similar differences between the cohort group and propositi.

The sample will be stratified by age. With a total of 284 children, we will have approximately 47 randomised to each treatment arm in each strata. Given that the standard deviation of the number of sore throats per year is estimated at approximately 2.0¹⁸, we will be able to estimate the difference between treatments in each strata with a standard error of 0.41. (Equivalently we would have 90% power to detect a difference of 1.35 episodes of sore throat per year in each strata assuming a type 1 error of 0.05).

It is anticipated that the difference in outcome between the two arms of the trial will be approximately 2 episodes in the second year of follow up. A sample size of 142 children in each arm should enable us to measure this difference with sufficient precision to undertake a meaningful economic analysis.

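### Section 10.2.1 fixes a Poisson error for the sore-throat count with no provision for extra-Poisson variation, which the planning SD of 2.0 implies in any arm averaging fewer than 4 episodes a year

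*Protocol*

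**What the plan says.** Section 3.4 of the Protocol defines the endpoint: "The primary clinical outcome is the reported number of episodes of sore throat in the two years after randomisation".

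Section 10.2.1 gives the model: "This variable will be analysed using generalised linear modelling assuming a Poisson error structure with a log link function". It then says that "interval estimates of the effect of tonsillectomy (in each of the first two years of follow up) will be generated" and that these estimates go into the economic analysis. For the other outcomes, "A Poisson error structure will be assumed for data in the form or a count". The section names no dispersion parameter, robust variance or negative binomial alternative.

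Section 10.1 takes the SD of sore throats per year as about 2.0 and expects that "the difference in outcome between the two arms of the trial will be approximately 2 episodes in the second year of follow up". It gives no expected mean for either arm during follow-up.

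**The concern.** A Poisson error sets the variance of each child's count equal to its mean. If the true variance is larger, the rate ratio is still estimated sensibly. Its standard error, however, is too small, the interval too narrow and the p-value too low.

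The planning figures point that way. An SD of 2.0 in both arms, means about 2 apart and a Poisson variance in each arm cannot all be true: a variance of 4 is Poisson at only one mean, 4 per year. The design adds further sources of extra variation. Section 10.2.2 supposes that severity matters, and section 2.2 asks whether outcome differs by age. Intention to treat keeps controls who are later operated on in the control arm, which makes that arm a mixture. The primary outcome also adds two years from the same child, and those years are probably positively correlated.

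The consequences go beyond the primary test. Under section 9.1.1.5, statistical significance decides between a cost-minimisation framework and incremental ratios. Section 10.2.2 uses the same model to look for severity effects, where false positives are the main hazard.

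**Working it through.** **Inputs.** From section 10.1: SD 2.0 per year, anticipated difference 2 episodes, 142 children per arm, about 47 per arm in each age stratum. Assumed, because the Protocol gives neither: the mean per year in each arm, and the correlation ρ between a child's two years.

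**1. The plan's own figures.** Standard error per stratum = 2.0 × √(2/47) = 0.413, against the stated 0.41. For a difference of 1.35: 1.35/0.413 − 1.96 = 1.31, so power is about 90.5%, against the stated 90%. Both reproduce, and they use SD 2.0 in each arm. The stated effect size of about 1.0 equals 2/2.0.

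**2. Dispersion in one arm, one year.** φ = variance/mean = 4/m.

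| Mean per year | 1 | 2 | 3 | 4 | 5 | 6 |
|---|---|---|---|---|---|---|
| φ | 4.0 | 2.0 | 1.33 | 1.0 | 0.80 | 0.67 |

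The arm is over-dispersed below 4, exactly Poisson at 4 and under-dispersed above 4.

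**3. Interval for the one-year rate ratio.** For control mean m0 and surgery mean m1, the ratio of true to Poisson variance of the log rate ratio is R = (4/m0² + 4/m1²)/(1/m0 + 1/m1). Coverage of the nominal 95% interval is 2Φ(1.96/√R) − 1. Each pair below differs by the anticipated 2 episodes.

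| Means | True / Poisson variance | R | SE ratio √R | Coverage |
|---|---|---|---|---|
| 3 v 1 | 4.444 / 1.333 | 3.33 | 1.83 | 72% |
| 4 v 2 | 1.250 / 0.750 | 1.67 | 1.29 | 87% |
| 5 v 3 | 0.604 / 0.533 | 1.13 | 1.06 | 93% |
| 6 v 4 | 0.361 / 0.417 | 0.87 | 0.93 | 96.5% |

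**4. The two-year total.** The variance of the total is 4 + 4 + 2ρ × 4 = 8(1 + ρ), and the mean is 2m. R is therefore multiplied by (1 + ρ).

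- ρ = 0.5: 5 v 3 gives 1.13 × 1.5 = 1.70, coverage 87%; 6 v 4 gives 0.867 × 1.5 = 1.30, coverage 91%.
- ρ = 0.3: coverage about 89% and 93.5%.
- At 6 v 4, R stays at or below 1 only if ρ is at most 1/0.867 − 1, about 0.15.

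**5. Type I error, one year, common mean m.** 2[1 − Φ(1.96/√(4/m))] is about 9% at m = 3 and 5% at m = 4.

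**6. Power with the full variance.** SE = 2.0 × √(2/142) = 0.237. For 1 episode per year, 1/0.237 − 1.96 = 2.25, so power is about 99%.

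**The case against.** The strongest reply is that an SD does not establish over-dispersion without a mean, and the Protocol states none for follow-up. Entry requires at least 4 episodes in each of two years or at least 6 in one (section 4.2.1). If such rates persisted, a one-year control count with SD 2.0 would have φ of 1 or less. If 2.0 is a figure pooled across arms, Poisson arms averaging 5 and 3 would produce it, since (5 + 3)/2 = 4. This stands, and it is why the size is conditional.

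It does not remove the point, for two reasons. Entry rates are a poor guide to follow-up means. Section 1.1 says that impressive histories are often not confirmed on close scrutiny. Section 1.3 says that the condition may be self-limiting, and cites a study whose children had only 3 to 4 episodes a year before surgery. Further, even if each year's count were exactly Poisson, the two-year total would have φ = 1 + ρ. At ρ = 0.5 that is 1.5, or coverage of about 89%.

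A second reply is that generalised linear modelling allows an estimated scale, and that a statistical analysis plan may add one. That is possible, but the Protocol names the error structure and says nothing that relaxes it.

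A reader might infer more than the document supports:

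- *Appendix 2 gives the expected means.* Its 1–2 episodes a year after treatment, and its 6–7 in the other health state, are vignettes for preference interviews, not analysis assumptions.
- *Type I error reaches 17% or 23%.* Those figures need a common mean of 2.0 or 1.5. Type I error concerns no treatment effect, so both arms should sit at the control level, not at a post-surgery level.
- *The school-absence SD shows the same thing.* The phrase "Given a reported standard deviation of 4.5" concerns days missed, whereas section 10.2.1 speaks of episodes: "A Poisson error structure will be assumed for data in the form or a count (such as the number of episodes of absence from school". These are different variables, and neither has a stated mean.
- *Incomplete diaries are counted as complete.* Section 9.1 expects that "with appropriate telephone reminders 90% of diaries will be returned completed" and gives no sign that return will differ by arm. Handling of exposure time is detail that an analysis plan commonly supplies.

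**Conclusion.** The point holds in conditional form. The Protocol commits the primary count, and every other count, to a Poisson error with no allowance for extra-Poisson variation. Its own planning SD is incompatible with that error in any arm averaging fewer than 4 episodes a year, and the surgery arm is likely to be one.

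Across pairs of means 2 apart, one-year coverage runs from about 72% (3 v 1) to 96.5% (6 v 4). For the two-year total with ρ = 0.5, it is about 87% at 5 v 3 and 91% at 6 v 4. These figures rest on SD 2.0 holding in each arm at every mean, and on assumed means and correlation.

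A reader might conclude that the intervals are certain to be too narrow. The document does not support that: with means of about 4 or more in both arms and little between-year correlation, the Poisson interval is adequate or slightly conservative. Nor is the primary conclusion clearly at risk. At the anticipated effect size of about 1.0, correct standard errors would still leave ample power. The exposure is greater for interval width, the secondary and severity analyses, and the economic inputs.

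**What to change.** In section 10.2.1, replace the Poisson error structure with negative binomial regression, or keep Poisson and state that the dispersion parameter will be estimated or robust standard errors used. If both years are fitted in one model, add a child-level random effect or use GEE. Apply the same rule to all count outcomes and to the severity analysis in section 10.2.2.

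This changes wording only, with no effect on data collection or sample size. Where counts are over-dispersed, intervals become somewhat wider. The power calculation above already uses the full SD of 2.0, so the trial keeps about 99% power for a difference of 1 episode per year with 142 per arm.

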6.2 Control

Non-surgical conventional medical treatment only will be used. There will be no active intervention protocol since no single prescribing strategy would be able to cover all patients³⁴. The referring GP will be free to treat as in their current practice. The use of usual treatment rather than an active intervention protocol is considered important for the implementation of study findings since 'surgical enthusiasts' may argue against the findings were the control group to be atypically and over rigorously treated

7 Randomisation

Independent world wide web based computer randomisation will allocate participants to treatment arms. Randomisation will take place once informed consent to the study has been completed and base-line data collected. The sample will be stratified by age of child at last birthday. Blocked randomisation will be used to ensure that within each centre, within each of the three age groups (4-7, 8-11, 12-15) children will be allocated in equal numbers to each arm of the trial. Where trial sites are unable to access the world wide web they will telephone the coordinating centre (University of Newcastle) in order for web based randomisation to be completed on their behalf.

Sampling for the cohort study will similarly be stratified by age.

8 Blinding

Health technology assessment is essentially a pragmatic activity conducted in normal clinical practice, rather than an exploratory activity conducted in highly controlled settings. It follows that blinding doctors and patients to treatment is not desirable since it distorts normal clinical practice. Nor is it practicable. In contrast, blinding assessors is important because it minimises subjective bias towards a given treatment. All research staff conducting interviews or processing postal questionnaires and diaries will be blind to treatment modalities of all participants. This will be facilitated by separating the responsibility for recruitment and randomisation from outcome assessment. Furthermore, participants will be encouraged to respond to questions without describing their treatment regime. In this way, we will minimise subjective bias towards a given treatment.

9 Data

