| Consultation rates and prescriptions | GP records | End of 24 month follow-up period | General practices |
| Consumer satisfaction | Questionnaire to children and parents | Base-line, 3, 12 and 24 months | Participant's home |
| Health-related quality of life | PedsQL ³⁵ questionnaire to children and parents | Base-line, 3, 12 and 24 months | Participant's home |

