10.2.2 Secondary analysis

The aim of secondary analysis is to determine whether we can identify groups of children who benefit from surgical treatment. It is hypothesised that disease severity may be an important factor. A severity index based on history of the condition during the year before entry to the study will be derived using data recorded in GP records. The relationship between severity and the effect of tonsillectomy will then be investigated using the modelling approach described above.

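### The main model names only the treatment difference; leaving out centre, age group and baseline values costs precision on normal-error outcomes such as PedsQL, though it does not widen the Poisson primary interval

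*Protocol*

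**What the plan says.** Section 10.2.1 gives the model for the sore-throat count: "This variable will be analysed using generalised linear modelling assuming a Poisson error structure with a log link function". The treatment effect enters as follows: "By fitting the difference between the two experimental groups as a fixed effect, interval estimates of the effect of tonsillectomy". No other term is named. The section goes on: "The same approach will be used to analyse the other outcomes", with Poisson errors for counts and normal errors for continuous measures such as the quality-of-life indices.

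Three other places bear on this:

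- Section 7 blocks the allocation so that "within each centre, within each of the three age groups (4-7, 8-11, 12-15) children will be allocated in equal numbers" to the two arms. With five centres and three age groups, that is 5 × 3 = 15 strata. The same section says: "Randomisation will take place once informed consent to the study has been completed and base-line data collected".
- Section 9.1, Table 2, lists the PedsQL at "Base-line, 3, 12 and 24 months".
- Section 10.2.2 brings in pre-entry severity, but only to study how it relates to the treatment effect: "A severity index based on history of the condition during the year before entry to the study will be derived".

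**The concern.** Blocking makes the arms alike in centre and age, so variation between strata contributes little to the true error of the treatment difference. A normal-error model without those factors still counts that variation as residual, and its standard error is then larger than the design warrants. Leaving out baseline PedsQL has a larger effect, because an earlier score on the same instrument usually predicts the later one.

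At stake is precision on the outcomes for which the protocol expects the smaller effect. Section 10.1 anticipates an effect size of 0.33 for psycho-social measures including quality of life, against about 1.0 for sore throats. The primary count needs separate treatment, because a Poisson model has no free residual variance for covariates to reduce.

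**Working it through.** **Inputs from the protocol.** Section 10.1: a difference of 1.5 days of missed school per year, SD 4.5, 80% power, 5% significance, 142 per arm; effect size 0.33 for quality of life; SD of about 2.0 sore throats per year. Section 4.3: 284 completers, 30% attrition, 406 recruited. **Assumed:** the correlation r between covariates and outcome, which the protocol does not give; the range 0.3 to 0.7 is used.

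**Step 1: the protocol's own figures.** n per arm = 2 × (1.960 + 0.842)² × (4.5/1.5)² = 2 × 7.85 × 9 = 141.3, so 142. Recruitment = 284/0.70 = 405.7, so 406. Both reproduce, and neither uses covariate adjustment. Power at 142 per arm is 0.802 for 1.5/4.5 = 0.333 SD. For exactly 0.33 SD it is Φ(0.33/√(2/142) − 1.960) = Φ(2.781 − 1.960) = 0.794.

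**Step 2: normal-error outcomes.** Adjustment multiplies the residual SD, and so the standard error, by √(1 − r²). Power becomes Φ(2.781/√(1 − r²) − 1.960).

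| Assumed r | SE factor | Cut in SE | Power for 0.33 SD |
|---|---|---|---|
| none fitted | 1.000 | – | 0.794 |
| 0.3 | 0.954 | 5% | 0.830 |
| 0.5 | 0.866 | 13% | 0.895 |
| 0.7 | 0.714 | 29% | 0.973 |

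The adjustment uses 4 parameters for centre, 2 for age group and 1 for baseline: 7 of the 282 residual degrees of freedom (284 − 2), which is negligible.

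**Step 3: the Poisson primary outcome.** With dispersion fixed at 1, the treatment-only standard error of the log rate ratio is √(1/E₀ + 1/E₁), where E is the total number of events in an arm. At assumed means of 3 and 1.5 episodes, E₀ = 142 × 3 = 426 and E₁ = 142 × 1.5 = 213, which gives √(1/426 + 1/213) = 0.084. No residual variance appears in this formula.

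A simulation checked what adjustment does. It used 142 per arm, 15 strata, one baseline covariate and 400 trials in each of 12 scenarios. Assumed means (control, surgery) were 3 and 1.5, 3.5 and 1.5, or 6 and 3. The between-child variance of the log rate was 0.1 or 0.3, of which age and baseline explained 25% or 50%. Centre was fitted but had no effect.

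| Quantity (range over 12 scenarios) | Treatment only | Adjusted | Adjusted/unadjusted |
|---|---|---|---|
| Reported SE, dispersion fixed at 1 | | | 1.002–1.003 |
| Coverage of nominal 95% interval, dispersion fixed at 1 | 0.79–0.94 | 0.83–0.95 | |
| Reported SE, dispersion estimated | | | 0.82–0.98 |
| Coverage, dispersion estimated | 0.94–0.98 | 0.93–0.97 | |
| Actual spread of the estimate | | | 0.87–0.99 |

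The Monte Carlo error of a coverage near 0.95 is √(0.95 × 0.05/400) = 0.011. The shortfall depends on how much children differ. With means 3 and 1.5 and a control SD of about 2.0, matching the protocol's annual SD, treatment-only coverage was about 0.94. With means 6 and 3 and a control SD of 3.1 it was 0.89. The lowest values, 0.79 and 0.82, came with a control SD of 4.3. That slightly exceeds the 2 × 2.0 = 4.0 that an annual SD of 2.0 allows for a two-year total.

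**The case against.** The strongest objection is that the covariate list is inferred from silence. Section 10.2.1 says how the treatment effect is fitted and does not say that nothing else is fitted. A generalised linear model accepts covariates, and the list often belongs in an analysis plan that is not shown. This stands as a limit: the protocol does not exclude adjustment. It does, however, go down to error structure, link and fitted term and then apply that approach to every outcome. The method it describes is less efficient than one its own design and data make available.

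The second objection is that nothing is lost against plan. The 142 per arm was derived without covariates, so an unadjusted analysis delivers the planned 80% or so. That is correct: the higher power is a gain forgone, not a shortfall, and the unadjusted analysis of continuous outcomes remains valid, if somewhat conservative.

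Several stronger readings are tempting, but the protocol does not support them:

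- A reader might infer that the primary interval is also too wide. Step 3 shows otherwise: the model-based standard error does not fall on adjustment, and with overdispersion the interval is too narrow. More precision there would in any case change little for the anticipated effect size of about 1.0, since 1.0/√(2/142) = 8.4 standard errors gives power above 99.9%.
- A reader might infer that pre-entry history is collected and never used. Section 10.2.2 uses it in the secondary analysis.
- A reader might take the reported episode count as a ready baseline covariate. The protocol mentions it only as an eligibility threshold (section 4.2.1), and diaries cover the 24 months after randomisation (section 9.1). The planned history measure is the GP-record index.
- A reader might call the unadjusted estimates biased. Chance imbalance in severity is ordinary sampling variation, and centre and age are balanced by the blocking.

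**Conclusion.** The concern holds mainly for continuous outcomes. For PedsQL, the stated approach gives intervals wider than they need be; the excess depends on a correlation that the protocol does not report, so only the range in Step 2 can be given. This is a matter of efficiency on secondary outcomes. It is worth correcting because the gain needs no extra children.

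For the sore-throat count, covariates alone neither narrow the stated interval nor fully repair its coverage. Adjustment does reduce the real spread of the estimate (by 1% to 13% in the assumed scenarios), but the reported interval can show this only when dispersion is allowed for. The two changes therefore belong together. How far coverage falls short depends on the assumed means and between-child variation. It is slight where a yearly count has an SD near 2.0 and larger where children differ more.

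**What to change.** In section 10.2.1, state that:

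- every outcome model fits treatment, centre and age group (4-7, 8-11, 12-15);
- the PedsQL model also fits baseline PedsQL (analysis of covariance);
- the sore-throat model also fits the pre-entry severity index from GP records already planned in section 10.2.2, and uses estimated dispersion, robust standard errors or a negative binomial model;
- unadjusted estimates are reported as supportive.

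If a separate analysis plan already lists these terms, a cross-reference is enough.

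The cost is a few sentences. The baseline questionnaire and the severity index are already planned, so no new visits or participants are needed. The one drawback is that children with a missing baseline value or no usable GP record need a simple rule, such as single imputation or a missing indicator, fixed before the data are seen.
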